3.2 Exclusion Criteria

Participants who exhibit any of the following conditions at screening will not be eligible for admission into the study.

CONFIDENTIAL

This document is confidential. Do not disclose or use except as authorized.

- 3.2.1 Prior treatment with an HSP90 inhibitor (e.g. 17-AAG, IPI-504, AUY922, STA-9090 (ganetespib) etc.)
- 3.2.2 Prior treatment with fulvestrant.
- 3.2.3 Participants may not be receiving any other investigational agents.
- 3.2.4 Concurrent treatment with commercial agents or other agents with the intent to treat the participant's malignancy, including endocrine therapy, chemotherapy, and/or targeted therapy, with the exception of bisphosphonates and GnRH agonists, as detailed in Section 3.1.8 and 3.1.10.
- 3.2.5 Untreated or progressive brain metastases. Patients with treated brain metastases not requiring chronic corticosteroids for symptom control are eligible.
- 3.2.6 Pending visceral crisis, in the opinion of the treating investigator.
- 3.2.7 History of allergic reactions attributed to compounds of similar chemical or biologic composition to fulvestrant or ganetespib.
- 3.2.8 Uncontrolled intercurrent illness including, but not limited to ongoing or active infection, or psychiatric illness/social situations that would limit compliance with study requirements.
- 3.2.9 Serious cardiac illness, defined as follows:
- Clinically unstable cardiac disease, including unstable atrial fibrillation, symptomatic bradycardia, unstable congestive heart failure, active myocardial ischemia, or indwelling temporary pacemaker
 - Ventricular tachycardia or a supraventricular tachycardia that requires treatment with a Class Ia antiarrhythmic drug (e.g., quinidine, procainamide, disopyramide) or Class III antiarrhythmic drug (e.g. sotalol, amiodarone, dofetilide). Use of other antiarrhythmic drugs is permissible.
 - Use of medications that have been linked to the occurrence of torsades de pointes (see Appendix I for a list of such medications). Investigators should note that Zofran (ondansetron) has been linked to QTc prolongation and the occurrence of torsades de pointes. Therefore it should not be used in patients being treated with ganetespib. The use of all other serotonin 5 HT3 antagonists is acceptable (e.g., palonsetron, granisetron, tropisetron).
 - Second- or third degree atrioventricular block (AV block) unless treated with a permanent pacemaker.
 - Complete left bundle branch block (LBBB)

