5.4 General Concomitant Medication and Supportive Care Guidelines

Medications taken prior to Cycle 1, Day 1 and during the study will be collected and noted in the medical record. The following are the supportive care guidelines for the study. The guidelines apply to all Arms of the study, except as otherwise noted:

- For patients receiving ganetespib, it is preferred not to use concomitant use of medications that are associated with a high incidence of QT prolongation (e.g., quinolones and ondansetron). See Appendix I for a list of medications that are known to predispose to Torsades de Pointes.
- No other antineoplastic agents will be permitted during this study, with the exception of bisphosphonates and GnRH agonists under the guidelines as specified in Section 3.1.8 and 3.1.10.
- No concurrent radiation treatment will be permitted during this study
- No treatment with chronic immunosuppressants (e.g., cyclosporine following transplantation or systemic steroids for treatment of autoimmune disease) will be permitted during this study; however, use of inhalant steroids and steroids given for antiemetic purposes are permitted
- For patients receiving ganetespib, caution should be exercised when concomitant medications that are cleared predominantly by the CYP3A4 or CYP2C19 pathways are administered. Examples of compound classes metabolized predominantly by CYP3A4 or CYP2C19 are provided below:
 - CYP3A4 substrates: benzodiazepines (e.g. midazolam), anticonvulsants (e.g. carbamazepine), calcium channel blockers (e.g. felodipine, nifedipine), antineoplastics (e.g. vincristine), macrolide antibiotics (e.g. erythromycin) and HIV antiviral agents.
 - CYP2C19 substrates: proton pump inhibitors (e.g. omeprazole) and antidepressants (e.g. sertraline).

The above information is precautionary only. Investigators are encouraged to discuss the use of individual medications with the Principal Investigator on a case-by-case basis.

CONFIDENTIAL

This document is confidential. Do not disclose or use except as authorized.

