5.5 Supportive Care Guidelines

Patients should receive full supportive care, including antiemetics, blood transfusions, intravenous fluid, etc., as clinically appropriate. The reason(s) for treatment, dosage, and dates of treatment should be recorded in the medical record.

Antiemetics

Patients may be given antiemetics at the discretion of the treating physician.

Anti-infectives

Antibiotics may be used at the discretion of the treating physician. If there is a reasonable alternative, it is preferred that quinolones and other agents that may prolong QTc are avoided.

Bisphosphonates

Oral or intravenous bisphosphonate treatment is allowed if the first dose was given prior to initiation of protocol therapy. Patients already receiving bisphosphonate therapy at the time of study entry may continue the treatment. Patients with new bone metastases documented as part of study screening procedures may begin a bisphosphonate, provided the first dose is given prior to initiation of protocol-based therapy. Bisphosphonates may not be started after the initiation of protocol-based therapy.

Growth factors

Patients may receive erythropoietin or other specific red blood cell growth factors and red blood cell transfusions will be permitted as clinically indicated during the study.

Patients may receive bone marrow colony stimulating factors (such as granulocyte colony-stimulating factor or granulocyte-macrophage colony-stimulating factor) as clinically indicated during the study.

If an Investigator determines a patient is at risk for severe neutropenia or febrile neutropenia, granulocyte-colony stimulating factor (G-CSF) may be used prophylactically beginning with the first cycle. G-CSF prophylactic use is recommended during subsequent treatment cycles in case of neutropenia lasting more than 7 days, febrile neutropenia, or documented infection with neutropenia.

Diarrhea management guidelines

Many patients will experience diarrhea, and some patients may experience Grade 3 or 4 diarrhea. The following proactive and ongoing management principles are necessary to avoid more serious complications of diarrhea. However, guidelines such as these should never replace sound clinical judgment.

Experience suggests that diarrhea is an expected drug class effect for Hsp90 inhibitors and it typically starts 2-3 hours following administration of ganetespib in most patients. However,

CONFIDENTIAL

This document is confidential. Do not disclose or use except as authorized.

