when appropriately managed with anti-diarrhea treatment, it is generally mild to moderate and its duration limited to 24 hours.

Due to the risk of diarrhea while receiving ganetespib, all patients will be educated to use prophylactic medication (Lomotil® or Imodium®) before ganetespib administration and before the onset of gastrointestinal symptoms to mitigate the severity and duration.

Suggested prophylaxis regimens are as follows:

- Loperamide (Imodium®): Start dosing (2mg) 1-2 hours **before** ganetespib infusion and continue with 2 mg every four hours for 12 hours. This treatment may be continued for up to 24 hours in the absence of symptoms of diarrhea. Due to inter-patient variability, adjustment to this regimen should be made on a case-by-case basis. The maximum dosage of loperamide is 16 mg/24 hrs.
- Dietary counseling: foods/liquids and quantities to intake or avoid

Guidelines for Treatment of Diarrhea (Active Management):

- In the event of diarrhea, patients will take loperamide at an initial 4 mg dose followed by 2 mg doses every 4 hours. In the presence of uncomplicated grade 1 or 2 diarrhea, loperamide will be continued until the patient is free from diarrhea for 12 hours. Total daily dose may not exceed 16 mg (8 capsules)
- If mild to moderate diarrhea persists after 24 hours despite treatment with loperamide, a cocktail of atropine-diphenoxylate (lomotil) or equivalent and loperamide may be considered. Loperamide 2 mg may be alternated with one tablet of Lomotil every 3 hours.
- For grade 3 or 4 diarrhea or complicated grade 1 or 2 (severe cramping, severe nausea/vomiting, decreased PS, fever, sepsis, grade 3 or 4 neutropenia, frank bleeding, dehydration), IV fluids will be used as appropriate, as well as prophylactic antibiotics. Hospitalization is recommended.
- Grade 1-2 : Loperamide 4mg first dose, then 2 mg every 4 hours until free from diarrhea for 12 hours
- If Grade 1 or 2 diarrhea persists for more than 24 hours: Loperamide 2mg q 2 hrs
- If Grade 1 or 2 diarrhea persists after 48 hours: Start 2L agents: a cocktail of Dyphenoxylate and atropine sulfate (Lomotil®). Alternate 2 mg loperamide with one tablet of Lomotil every 3 hours.
- Grade 3 or 4 or Complicated Grade 1 or 2: IV fluids as appropriate.

Management of hypersensitivity reactions

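### Safety text conflicts in three places: the restart dose after grade 4 toxicity (6.2.1), torsades-linked drugs (5.4 and 5.5 against 3.2.9 and 5.6.2) and, less seriously, loperamide dosing (5.5)

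*Combined protocol and SAP*

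**What the plan says.** **Grade 4 toxicity (Section 6.2.1).** The dose-level table lists 200, 175 and 150 mg/m². In the modification table, the diarrhea row and the other non-hematologic row both cover grade 3 and above, and both end in a one-level reduction. The row for a third or later nausea/vomiting episode shows grade 3 in its grade column, but its action cell speaks of grade 3 or higher; it too reduces one level. The text after the table says that grade 4 toxicity, hematologic or not, leads to a restart at 150 mg/m². The section also forbids raising a dose once it has been lowered. Sections 5.6.2 and 6.2.1 add a separate dose of 120 mg/m² after a first QTc of 501 ms or more.

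**QT drugs.** For patients on ganetespib, Section 5.4 says "it is preferred not to use concomitant use of medications that are associated with a high incidence of QT prolongation (e.g., quinolones and ondansetron"). Section 5.5 says of antibiotics that, where there is a reasonable alternative, "it is preferred that quinolones and other agents that may prolong QTc are avoided", and of antiemetics that "Patients may be given antiemetics at the discretion of the treating physician". On ondansetron, Section 3.2.9 says "Therefore it should not be used in patients being treated with ganetespib", and Section 5.6.2 repeats this. Section 5.6.2 also bars any QT-prolonging drug linked to torsades, and asks for avoidance or caution with QT-prolonging drugs that are not so linked. Appendix I lists ondansetron, moxifloxacin and sparfloxacin (the last marked as no longer sold in the U.S.).

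**Loperamide (Section 5.5).** The prophylaxis bullet says "The maximum dosage of loperamide is 16 mg/24 hrs". The first treatment bullet gives "loperamide at an initial 4 mg dose followed by 2 mg doses every 4 hours" and repeats the 16 mg daily limit. A later bullet in the treatment list says "If Grade 1 or 2 diarrhea persists for more than 24 hours: Loperamide 2mg q 2 hrs". For diarrhea that continues on loperamide, one bullet allows the Lomotil combination after 24 hours and another starts it after 48 hours.

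**The concern.** In each pair one version is less protective, and a site that relies on it is following the protocol. A patient with grade 4 diarrhea at the starting dose could restart at 175 rather than 150 mg/m². A patient on ganetespib could be given ondansetron or moxifloxacin, although the background section reports a maximum mean QTcF increase of 21.5 ms at 24 hours. A patient could be told to take loperamide at an interval that passes the daily limit.

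These are routine decisions. Section 6.1.1 reports diarrhea in 72% of ganetespib patients, nausea in 37% and vomiting in 20%. The nursing education sheet sends staff to the dose tables of Section 6.2.1 without mentioning the grade 4 text below them, and to Section 5.5 for diarrhea.

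**Working it through.** **1. Grade 4 toxicity.** Inputs are the dose levels and rules of Section 6.2.1, and the 120 mg/m² dose from Sections 5.6.2 and 6.2.1. For diarrhea or other non-hematologic toxicity of grade 4:

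| Current dose (mg/m²) | Table row | Text below the table |
|---|---|---|
| 200 | 175 | 150 |
| 175 | 150 | 150 |
| 150 | no lower level listed | 150 as worded; the next sentence stops patients who cannot tolerate 150 |
| 120 (after QTc prolongation) | not a listed level | 150 |

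- From 200 by the table: (200 − 175)/200 = 12.5% reduction.
- From 200 by the text: (200 − 150)/200 = 25% reduction.
- From 120 by the text: (150 − 120)/120 = 25% increase, contrary to the ban on re-escalation.

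The table and text therefore disagree at 200 and agree at 175, and at 120 the text contradicts another rule of its own section. The fatigue, platelet, hemoglobin and neutropenia rows list grade 3 at most, so the grade 4 text is unopposed there. For grade 4 infusion reactions and grade 4 cardiac toxicity the table requires permanent discontinuation, while the text read literally would allow a restart at 150. Neither source is stricter throughout, so a bare statement that the text governs, or that the table governs, would not be safe.

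**2. QT drugs.**

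| Drug | 5.4 and 5.5 | 3.2.9 and 5.6.2 | Conflict |
|---|---|---|---|
| Ondansetron | preferably not used (5.4) | not to be used with ganetespib | yes |
| Moxifloxacin, sparfloxacin | preferably avoided, as quinolones | barred by 5.6.2 as torsades-linked (Appendix I) | yes; sparfloxacin of little practical weight |
| Quinolones not linked to torsades | preferably avoided | avoidance or caution (5.6.2) | no |

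The Section 5.4 bullet cites Appendix I itself, so it attaches permissive wording to the list of drugs that Section 5.6.2 bars.

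**3. Loperamide.** Doses are counted over 24 hours, with the first at hour 0 and the hour-24 dose left out.

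- Prophylaxis every 4 hours, continued to 24 hours: 6 × 2 = 12 mg.
- First treatment step: 4 + 5 × 2 = 14 mg.
- 2 mg every 2 hours: 12 × 2 = 24 mg, which is 24 − 16 = 8 mg over the limit (8/16 = 50%).
- 2 mg every 3 hours: 8 × 2 = 16 mg.

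In the later set of bullets the two-hourly step runs from 24 to 48 hours, so 24 hours at that interval is its natural length. If it follows a full first step, and a dose taken exactly 24 hours earlier is not counted, the rolling 24-hour totals at hours 0, 2, 4, 6, 8 and 10 of the step are 12, 14, 14, 16, 16 and 18 mg. The limit is first passed with the sixth dose, at hour 10. Counting the dose taken exactly 24 hours earlier moves this to the fifth dose, at hour 8. If the count restarts with the step, it is the ninth dose, at hour 16 (9 × 2 = 18 mg).

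**The case against.** **Grade 4.** The sentence specific to grade 4 comes after the table, and an ordinary reader would let the specific rule prevail. The nausea/vomiting row is also doubtful, because its grade column says 3. The second point stands, and that row is the weakest of the three. The first does not settle the matter. The other two rows expressly include grade 4, and letting the text prevail everywhere would override the discontinuation rules for infusion reactions and cardiac toxicity and raise the dose of a patient at 120 mg/m². A reader might also infer that the problem is confined to the starting dose; the 120 mg/m² case shows that it is not.

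**QT drugs.** A reader might infer that Section 5.6.2 prohibits quinolones as a class. It does not name them; only those linked to torsades are barred. A reader might also take the discretion over antiemetics as a conflict by itself. It is general supportive-care text for all arms, limited by the specific ondansetron rule for ganetespib patients. It is fair to add that the ondansetron statement sits in an exclusion criterion covered by the eligibility checklist, so a site is unlikely to miss it at entry. But Section 5.4 is what a site consults during treatment, and crossover patients start ganetespib only after progression on fulvestrant.

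**Loperamide.** A reader might infer that the two-hourly step has no cap. The documents do not support that: the limit is stated twice in Section 5.5, once as a maximum for the drug, and can be read over every step. What remains is an interval that cannot be kept for 24 hours within the limit, in a bullet that does not repeat it.

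**Weight.** A site that follows the stricter text breaches nothing, and Section 5.5 says its diarrhea guidelines do not replace clinical judgment. That lowers the stakes but does not tell a site which instruction applies.

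**Conclusion.** The inconsistencies are real and sit in current protocol text. The grade 4 rule matters most: a 12.5% or a 25% reduction from 200 mg/m² with no stated precedence, and a literal 25% increase from 120 mg/m². The QT conflict is complete for ondansetron, applies among quinolones only to those in Appendix I, and is absent for quinolones not linked to torsades. The loperamide point is minor: 24 mg against 16 mg if the interval is kept for a full day and the limit is not carried over, plus two Lomotil start times.

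The dose arithmetic assumes that each rule is followed as written; the hour at which the loperamide limit is passed also depends on the counting convention. How many patients would be affected cannot be derived from the documents. None of this touches the primary endpoint, power or alpha.

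**What to change.** 1. **Section 6.2.1.** Restrict the diarrhea, other non-hematologic and third-episode nausea/vomiting rows to grade 3 (keeping the prolonged or clinically significant grade 2 part of the non-hematologic row), and let the grade 4 sentence govern. Add that the dose is never raised, and that patients already at 150 or 120 mg/m² stop ganetespib. State that grade 4 infusion reactions and grade 4 cardiac toxicity remain permanent discontinuation.
2. **Sections 5.4 and 5.5.** For patients on ganetespib, prohibit the drugs in Appendix I, naming ondansetron and moxifloxacin. Keep the avoid-or-caution advice for QT-prolonging drugs that are not listed.
3. **Section 5.5, loperamide.** Add to the two-hourly bullet a ceiling of 16 mg in any 24 hours, counting loperamide already taken. Keep one start time for Lomotil.

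The cost is one wording amendment and a notice to sites. Sample size, schedule and analysis do not change.

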Ganetespib contains a surfactant (polysorbate 80) that has been associated with hypersensitivity reactions in other medications administered by infusion. Infusion type reactions associated with ganetespib (approximately 7% of patients) have been reported at doses of 10 to 200 mg/m². Symptoms included pruritus, flushing, shortness of breath, chest tightness, dizziness, headache, increased systolic blood pressure and heart rate. These events were mostly grade 1 and grade 2 and usually responsive to treatment with i.v. diphenhydramine HCl (Benadryl®) and steroids

CONFIDENTIAL

This document is confidential. Do not disclose or use except as authorized.

(sometimes with H2 blockers). In addition, subjects with infusion-type reactions usually could continue receiving ganetespib after pre-mediation with diphenhydramine HCl and steroids.

Based on IB Edition 9, premedication is required prior to ganetespib infusion for at least 2 cycles. Premedications include:

- Dexamethasone 10 mg IV, or therapeutic equivalents
- Diphenhydramine HCl 25-50 mg, or therapeutic equivalents
 - *Dose of diphenhydramine may be reduced per investigator discretion if patient experienced previous problems with 25mg or higher*

For patients who have successfully tolerated at least 2 cycles of ganetespib without a hypersensitivity reaction, routine premedication with dexamethasone and diphenhydramine prior to subsequent ganetespib infusions is not required and is left to the discretion of the treating provider.

If, despite premedication, an infusion hypersensitivity reaction to ganetespib is suspected, the following management is provided as guidance only; treatment will be based on clinical presentation. Institution specific premedication and/or treatment procedures and regimens may also be appropriate in lieu of these guidelines.

- **Mild and moderate symptoms:**

1. Stop ganetespib administration
2. Give i.v. diphenhydramine HCl (Benadryl[®]) 25-50 mg and dexamethasone 10 mg i.v.
3. After recovery from symptoms, resume ganetespib infusion or re-schedule patient for re-treatment; a reduced flow rate may be considered

In subsequent cycles, consider optimizing premedication regimen.

- **Severe symptoms** (i.e., hypotension requiring pressor therapy, IV fluids, angioedema, respiratory distress requiring bronchodilator therapy, generalized urticaria):

1. Stop ganetespib administration
2. Give intravenous dexamethasone and diphenhydramine HCl (Benadryl[®]) as above

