3. Add intravenous H2 blocker
4. Add adrenaline (1:1000) or bronchodilators as indicated
5. Reschedule dose administration for the following day
6. In subsequent cycles, consider optimizing premedication regimen.

If severe symptoms reoccur with optimal premedication, treatment with ganetespib should be discontinued permanently.

The following is an example of an optimized premedication regimen:

CONFIDENTIAL

This document is confidential. Do not disclose or use except as authorized.

- Dexamethasone 12 mg PO and diphenhydramine HCL 25-50 mg PO approximately 12-24 hours prior to the next dose of ganetespib
- Repeat dexamethasone 12 mg PO and diphenhydramine HCL 25-50 mg PO approximately 4-6 hours prior to the re-challenge

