	2	See Section 5.5	None; If unacceptable to patient or medically concerning despite maximal supportive measures, then skip until recovery to \leq grade 1 (or baseline), up to 21 days*. Restart at same dose**.
	≥ 3		If grade 3 or greater despite maximal supportive measures, skip until recovery to \leq grade 1 (or baseline), up to 21 days*. And then Reduce 1 dose level.
Nausea/vomiting	1 or 2	Treatment as appropriate.	None
	3 (First or 2 nd occurrence)	Treatment as appropriate.	Skip until recovery to \leq grade 1 (or baseline), up to 21 days*. And then Restart at same dose.
	3 (3 rd or more occurrence)		If grade 3 or higher despite optimal prophylactic measures, then skip until recovery to \leq grade 1 (or baseline), up to 21 days*. And then Reduce 1 dose level.
Fatigue	1	No intervention	None
	2	Treatment as appropriate.	None; If unacceptable to patient or medically concerning then hold until recovery to \leq grade 1 (or baseline), up to 21 days*. Restart at same dose**.
	3	Treatment as appropriate.	Skip until recovery to \leq grade 1 (or baseline), up to 21 days*. And then Reduce 1 dose level.
Other non-Hematologic toxicity	1	No Intervention	None
	2	Treatment as appropriate	None; If unacceptable to patient or medically concerning then skip until recovery to \leq grade 1 (or baseline), up to 21 days*. Restart at same dose**.
	2 prolonged or clinically significant and grade ≥ 3	Treatment as appropriate	Skip until recovery to \leq grade 1 (or baseline), up to 21 days And then Reduce 1 dose level*

CONFIDENTIAL

This document is confidential. Do not disclose or use except as authorized.

Toxicity	Grade	Guideline for management	Ganetespiib dose modification*
Infusion reactions	3	Treatment per institutional guidelines for infusion reactions	Contact Principal Investigator to determine whether patient may be retreated
	4	Stop infusion	Permanently discontinue
Thrombocytopenia	1 or 2	No intervention	None
	3	No intervention	Skip until recovery to \leq grade 1 (or baseline), up to 21 days And then Reduce 1 dose level*
Hemoglobin	1 or 2	Treatment as appropriate	None
	3	Treatment as appropriate	Skip until recovery to \leq grade 1 (or baseline), up to 21 days And then Reduce 1 dose level*
Neutropenia	1 or 2	No intervention	None
	3 (ANC < 1,000/ μ L) lasting > 7 days		Skip until recovery to \leq grade 1 (or baseline), up to 21 days And then Reduce 1 dose level*

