Study Drug & Administration	
Ganetespib administration guidelines are in Sections 5.2 and 7.1
 
 IV, diluted in D5W, administered over 1 hour using a 0.2µm inline filter – Section 7.1.7 Pre-med with dexamethasone and diphenhydramine is required for Cycle 1 and 2. Participants who have successfully tolerated at least 2 cycles of ganetespib ((on Arms B or C) without a hypersensitivity reaction are not required to take the pre meds and is left to the discretion of the treating provider described in Section 5 – see alert page. Loperamide is recommended – Section 5.2.1 Use of vascular access devices (VADs) w/silicone catheters ONLY or peripheral IV is permitted. Use of VADs with catheters made of any other material is prohibited – Sect. 5.2 Administered on Days 1, 8, and 15 of each cycle (3 weeks on, 1 week off) – Section 5.2 See Section 5.5 for management of hypersensitivity reactions 
Fulvestrant administration guidelines are in Sections 5.2 and 7.2
 
 Administered via intramuscular injection into the buttocks on C1, D1; C1, D15; and Day 1 of each subsequent cycle; Sect. 5.2.2 & 7.2.4. NOTE: In Arm C, will only be administered on Day 1 of each cycle; see Alert Page
Dose Modifications and Toxicity	
Dose Modification for toxicity guidelines are in Section 6
 
 Definition of DLT is outlined in Section 5.3 
Ganetespib: See Section 6.2.1 for Dose Reduction Table and Dose Modification Guidelines Table
 
 Diarrhea is expected in most patients. Please see Section 5.5 for diarrhea management guidelines (NOTE: These guidelines were updated on 10/2/2013). Toxicities must recover to ≤ Grade 1 or baseline to resume treatment after skipped doses Criteria to treat: ≤ Grade 2: ANC ≥ 1000/mm³; Platelets ≥ 50,000/ mm³; Hgb ≥ 8.0g/dL Participants may continue on fulvestrant alone if treatment with ganetespib must be discontinued 
Fulvestrant: There are no dose modifications for fulvestrant - See Section 6.2.2

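### Section 5.5 and the Section 6.2.1 table give inconsistent retreatment and discontinuation instructions for severe ganetespib infusion reactions, and nothing says which governs

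*Combined protocol and SAP*

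**What the plan says.** Section 5.5, under management of hypersensitivity reactions, has two tiers: mild and moderate symptoms, and severe symptoms. Severe is defined by examples: "hypotension requiring pressor therapy, IV fluids, angioedema, respiratory distress requiring bronchodilator therapy, generalized urticaria". The listed steps are to stop ganetespib, give dexamethasone and diphenhydramine, add an H2 blocker, add adrenaline or bronchodilators as indicated, and then "Reschedule dose administration for the following day". The stopping condition comes after the list: "If severe symptoms reoccur with optimal premedication, treatment with ganetespib should be discontinued permanently". The whole block is introduced with the statement that "the following management is provided as guidance only; treatment will be based on clinical presentation", and institutional procedures may replace it.

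The table in Section 6.2.1 has its own rows for infusion reactions, by grade. For Grade 3 the dose modification entry is "Contact Principal Investigator to determine whether patient may be retreated". For Grade 4 the management entry is "Stop infusion" and the dose modification entry is "Permanently discontinue".

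Below the table, a general paragraph on Grade 4 hematologic or non-hematologic toxicity says to skip ganetespib until recovery, for up to 21 days, and then resume at a reduced dose. It makes no exception for infusion reactions.

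The Nursing Protocol Education Sheet says "See Section 5.5 for management of hypersensitivity reactions". It also sends staff to Section 6.2.1 for dose reductions and modifications.

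**The concern.** Section 5.5 does more than describe acute care. It schedules the next dose and sets a threshold for permanent discontinuation, and both are dosing decisions that the Section 6.2.1 table also makes. The two places use different severity scales (symptom tiers and CTCAE grades), have different triggers for stopping (recurrence, or a first Grade 4 event), and differ on whether the Principal Investigator must decide before retreatment. On infusion reactions, neither refers to the other.

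A site that follows Section 5.5 as written could give ganetespib the next day to a patient for whom the table requires a central decision first. On one reading, it could do so for a patient whom the table takes off ganetespib. Another site, working from the table, would act differently after the same reaction. Recorded reasons for stopping ganetespib in Arms B and C could then depend on which section the site used.

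**Working it through.** No planned figure rests on this point, so there is none to reproduce. The check is a side-by-side reading.

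| Question | Section 5.5 | Section 6.2.1 table | Section 6.2.1, general Grade 4 paragraph |
|---|---|---|---|
| Severity scale | Mild/moderate and severe; no CTCAE grade | CTCAE Grades 3 and 4 | CTCAE Grade 4 |
| Grade 3, first event | If classed as severe: next-day dose, no Principal Investigator step | Principal Investigator decides whether to retreat | Not addressed |
| Grade 4, first event | No separate tier; if classed as severe, next-day dose | Permanent discontinuation | Skip until recovery, then reduced dose |
| Trigger for permanent stop | Recurrence of severe symptoms with optimal premedication | First Grade 4 event | Intolerance of the lowest listed dose, or no recovery within 21 days |

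**Step 1, Grade 3.** Both places allow retreatment to happen. They differ on the condition: the table requires a Principal Investigator decision, and Section 5.5 does not mention one. This difference holds on any reading in which severe includes Grade 3. Section 11.4 supports that reading, because it pairs Grade 3 with the word severe.

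**Step 2, Grade 4.** Section 5.5 never mentions Grade 4 or life-threatening reactions in this list. Section 11.4 describes Grade 4 as life-threatening or disabling, which suggests that severe stops at Grade 3. Against that, Section 5.5 has no higher tier, and its examples include hypotension needing pressors and respiratory distress. A Grade 4 reaction has nowhere else to go in that section. Both readings are open. On the wider one, the two places conflict directly at the first event.

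**Step 3, third instruction.** The general Grade 4 paragraph covers all non-hematologic toxicity without exempting infusion reactions. Read literally, it conflicts with the table's own Grade 4 row and, on the wider reading in Step 2, with Section 5.5.

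**Step 4, precedence.** Section 5 (opening text) and Section 5.2.1 place dose modifications in Section 6, and Section 6.2 calls its content rules. However, the opening of Section 6 calls the same content recommendations, and the lead-in to the table calls it guidelines. No sentence says which section governs an infusion reaction.

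**Step 5, size.** Section 5.5 reports infusion-type reactions in approximately 7% of patients, mostly Grade 1 or 2, at doses of 10 to 200 mg/m². If that rate applied here, reactions of any grade would number:

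- Arm B: 0.07 × 47 = 3.3
- Arm B plus all 24 Arm A patients, if every one crossed over: 0.07 × (47 + 24) = 5.0

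The documents give no rate for Grade 3 or 4 reactions. The number exposed to the inconsistency is therefore a fraction of these counts that cannot be derived, and it could be zero.

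**The case against.** The best defence is that the two sections have different jobs. Section 5.5 is supportive care, expressly guidance, and yields to clinical presentation and institutional practice. Section 6 is where the protocol says dose modifications are found. On acute treatment they agree, since the table's Grade 3 management entry also defers to institutional guidelines. Much of this stands, and a careful investigator would probably consult the table. It does not settle the matter, because Section 5.5 itself makes re-dosing and stopping decisions, and Section 6 is also described in non-binding terms.

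A reader might infer more than the text supports:

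- **That every severe reaction meets opposite instructions.** At Grade 3 the table leaves retreatment open, so the difference is a missing decision step. At Grade 4 the instructions are opposed only if severe in Section 5.5 includes Grade 4. Grading the listed symptoms would need the CTCAE text, which is not in the documents.
- **That infusion nurses are sent only to Section 5.5.** The nursing sheet points to both sections. Its defect is that it gives no order between them.
- **That 3 to 5 patients would be affected.** Those counts cover reactions of any grade. The Section 5.5 pathway also applies to reactions that occur despite premedication, which is required for at least the first 2 cycles.
- **That the primary analysis is compromised.** Patients who stop ganetespib without progression are to continue fulvestrant and stay under follow-up for progression (Sections 5 and 5.1.15). Section 14.2 analyses PFS by intention to treat whether or not treatment stopped early.

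**Conclusion.** The inconsistency is real and unresolved. At Grade 3, Section 5.5 omits the Principal Investigator decision that the table requires before retreatment; this assumes only that severe includes Grade 3. At Grade 4, the table discontinues at the first event, Section 5.5 can be read as allowing a next-day dose, and the general Grade 4 paragraph says something else again. The Section 5.5 part of that statement rests on its having no tier above severe. The conflict between the table row and the general paragraph does not depend on how severe is read.

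The number of patients concerned is unknown and probably small. The case for acting rests on what is at stake in a single event, re-exposure after a potentially life-threatening reaction, and not on frequency. No effect on the PFS analysis is shown. I take no view on which clinical rule is right.

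**What to change.** Reconcile the three texts in the next amendment:

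- Map the mild, moderate and severe tiers of Section 5.5 to CTCAE grades, with Grade 4 placed explicitly.
- Keep one retreatment and discontinuation rule for infusion reactions, chosen by the sponsor, and state in it whether and when the Principal Investigator must decide.
- State in both sections which one governs, with a cross-reference.
- Say whether the general Grade 4 paragraph applies to infusion reactions.
- Align the Nursing Protocol Education Sheet with the governing section.

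The cost is a wording change in Sections 5.5 and 6.2.1 and in the nursing sheet, with the IRB review that any amendment needs. It adds no patients and no study procedures.
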